**Confidential**

- **Implant or procedure aspects**

**Procedures:**

**Patient enrolled before planned pregnancy**

**Visit 1a**

- Inform the patient about study goals and procedures
- Ask the patient to sign and date the Patient Informed Consent form
- Ask patient to complete the HFS and DTSQs questionnaires
- Create a patient account in eCRF, and document the patient's ID code in the enrollment log
- Weigh the patient
- Measure the patient's blood pressure
- Collect the patient's medical data listed in the eCRF
- Check if the patient is properly trained on the loaned devices like the insulin pump, BG meter and sensor (if applicable)
- Document basal rate setting on the insulin pump
- Check the Bolus Wizard setting like the carbohydrate ratio, insulin sensitivity, target range, and active insulin time (if applicable)
- Check if the patient uses the reservoir and the infusion set as required
- If the patient is treated with SAP or she wants to use the sensor during the study period, make sure the patient is instructed on how to use the Continuous Glucose Monitoring feature of the pump, how to insert the sensor, and how to use the MiniLink transmitter
- Check if patient is aware of product support, and if necessary, give her the product helpline telephone number
- Fill in the eCRF and submit the data
- Create a CareLink Clinical account, and upload the data from the insulin pump (and BG meter, if applicable)

If the patient is not properly trained, retraining is required. Then follow these training guidelines:

**Patient training guidelines**

Patients have to be properly trained on how to use the insulin pump and the consumables. Training is provided by the Health Care Professional (HCP) from the investigation site, or a Certified Product Trainer (CPT) based on the local practice. The trainer follows the standard training checklist during the training. When the training is completed, the checklist has to be signed by the patient and the trainer, and filed in the investigation site file.

Patients who are selected for insulin pump therapy only (without the sensor), receive the Paradigm REAL-Time 722 insulin pump. They are trained for the use of the insulin pump, and they do not have to be instructed on the CGM related features of the insulin pump, unless they intend to purchase and use sensors during the study period.

Patients who are selected for SAP (insulin pump and sensor), receive the Paradigm Veo 754 insulin pump. They have to be trained for all features of the insulin pump including the continuous glucose monitoring (CGM) features.

**Product support, helpline**

Patients have to be trained on how to do basic troubleshooting, and they have to receive the Product Support (Helpline) phone number from the trainer. In case of device related problems, they should contact the Helpline.

This document is electronically controlled. Printed copies are considered uncontrolled.

**Confidential**

Sponsor representatives may perform study activities such as providing technical support and programming support during follow up.

**Back-up therapy**

In case of device failure, the patient should be able to switch to back-up therapy until replacement device is provided. It is recommended to keep syringes, insulin pens and insulin cartridges on hand as back-up.

**Pump start, pump settings**

Guidelines on how to start a patient on the insulin pump will be provided to investigation sites, and this document will be kept separately from the CIP.

**Visit 2a – visit during pregnancy: 12th week (± 4 weeks window)**

- Weigh the patient
- Measure the patient's blood pressure
- SAP treatment: If the patient has not used the sensor during the preconception period, make sure the patient is instructed on how to use the Continuous Glucose Monitoring feature of the Paradigm Veo insulin pump, how to insert the sensor, and how to use the MiniLink transmitter
- Collect the patient's medical data listed in the relevant eCRF
- Make therapy adjustment, and change pump settings, if necessary
- Check infusion site, make sure patient uses infusion sets properly
- Fill in the eCRF and submit the data
- Upload data into CareLink Clinical from the insulin pump (and BG meter, if applicable)

**Visit 2b – no conception in 12 months (± 2 weeks window)**

- Ask patient to complete the HFS and DSTQs questionnaires
- Weigh the patient
- Collect the patient's medical data listed in the relevant eCRF
- Fill in the eCRF and submit the data
- Upload data into CareLink Clinical from the insulin pump (and BG meter, if applicable)
- Terminate pump therapy

**Visit 3 – visit during pregnancy: 24th week (± 2 weeks window)**

- Ask patient to complete the HFS, DSTQs and DSTQc questionnaires
- Weigh the patient
- Measure the patient's blood pressure
- Collect the patient's medical data listed in the relevant eCRF
- Make therapy adjustment, and change pump settings, if necessary
- Check infusion site, make sure patient uses infusion sets properly
- Fill in the eCRF and submit the data
- Upload data into CareLink Clinical from the insulin pump (and BG meter, if applicable)

**Visit 4 – visit during pregnancy: 36th week (± 2 weeks window)**

- Ask patient to complete the HFS and DSTQs questionnaires

This document is electronically controlled. Printed copies are considered uncontrolled.

**Confidential**

- Weigh the patient
- Measure the patient's blood pressure
- Collect the patient's medical data listed in the relevant eCRF
- Make therapy adjustment, and change pump settings, if necessary
- Check infusion site, make sure patient uses infusion sets properly
- Fill in the eCRF and submit the data
- Upload data into CareLink Clinical from the insulin pump (and BG meter, if applicable)

#### **Visit 5 – optional visit after delivery (+ 2 weeks window)**

- Weigh the patient before and after delivery
- Collect the delivery data listed in the relevant eCRF
- Collect the neonatal outcome data listed in the relevant eCRF
- Fill in the eCRF and submit the data
- Upload data into CareLink Clinical from the insulin pump (and BG meter, if applicable)

#### **Visit 6 – 6 weeks after delivery ( $\pm$ 2 weeks window)**

- Ask patient to complete the HFS and DTSQs questionnaires
- Weigh the patient
- Measure the patient's blood pressure
- Collect the patient's medical data listed in the relevant eCRF
- Fill in the eCRF and submit the data
- Upload data into CareLink Clinical from the insulin pump (and BG meter, if applicable)
- Terminate pump therapy

#### **Miscarriage – any time**

- Weigh the patient
- Measure the patient's blood pressure
- Collect the patient's medical data listed in the relevant eCRF
- Discuss with patient if she wants to continue the same therapy (CSII or SAP)
- Check infusion site, make sure patient uses infusion sets properly (if applicable)
- Make therapy adjustment, and change pump settings, if necessary
- Fill in the eCRF and submit the data
- Upload data into CareLink Clinical from the insulin pump (and BG meter, if applicable)

#### **Early dropout – any time**

- Ask patient to complete the HFS and DTSQs questionnaires, if patient agrees
- Weigh the patient
- Measure the patient's blood pressure
- Collect the patient's medical data listed in the relevant eCRF
- Discuss with patient if she wants to continue the same therapy (CSII or SAP)
- Check infusion site, make sure patient uses infusion sets properly (if applicable)
- Make therapy adjustment, and change pump settings, if necessary
- Fill in the eCRF and submit the data

This document is electronically controlled. Printed copies are considered uncontrolled.

**Confidential**

- Upload data into CareLink Clinical from the insulin pump (and BG meter, if applicable)

### **Patient enrolled during pregnancy, up to the 16th week**

#### **Visit 1b (up to 16th week of pregnancy)**

- Inform the patient about study goals and procedures
- Ask the patient to sign and date the Patient Informed Consent form
- Ask patient to complete the HFS and DTSQs questionnaires
- Create a patient account in eCRF, and document the patient's ID code in the enrollment log
- Weigh the patient
- Measure the patient's blood pressure
- Collect the patient's medical data listed in the eCRF
- Check if the patient is properly trained on the loaned devices like the insulin pump, BG meter and sensor (if applicable)
- Document basal rate setting on the insulin pump
- Check the Bolus Wizard setting like the carbohydrate ratio, insulin sensitivity, target range, and active insulin time (if applicable)
- Check if the patient uses the reservoir and the infusion set as required
- If the patient is treated with SAP or she wants to use the sensor during the study period, make sure the patient is instructed on how to use the Continuous Glucose Monitoring feature of the pump, how to insert the sensor, and how to use the MiniLink transmitter
- Check if the patient is aware of product support, if necessary, give her the product helpline telephone number
- Fill in the eCRF and submit the data
- Create a CareLink Clinical account, and upload the data from the insulin pump (and BG meter, if applicable)

If the patient is not properly trained, retraining is required. Then follow these training guidelines:

#### **Patient training guidelines**

Patients have to be properly trained on how to use the insulin pump and the consumables. Training is provided by the Health Care Professional (HCP) from the investigation site, or a Certified Product Trainer (CPT) based on the local practice. The trainer follows the standard training checklist during the training. When the training is completed, the checklist has to be signed by the patient and the trainer, and filed in the investigation site file.

Patients who are selected for insulin pump therapy only (without the sensor), receive the Paradigm REAL-Time 722 insulin pump. They are trained for the use of the insulin pump, and they do not have to be instructed on the CGM related features of the insulin pump, unless they intend to purchase and use sensors during the study period.

Patients who are selected for SAP (insulin pump and sensor), receive the Paradigm Veo 754 insulin pump. They have to be trained for all features of the insulin pump including the continuous glucose monitoring (CGM) features.

#### **Product support, helpline**

Patients have to be trained for how to do basic troubleshooting, and they have to receive the Product Support (Helpline) phone number from the trainer. In case of device related problems, they should contact the Helpline.

This document is electronically controlled. Printed copies are considered uncontrolled.

**Confidential**

Sponsor representatives may perform study activities such as providing technical support and programming support during follow up.

**Back-up therapy**

In case of device failure, patient should be able to switch to back-up therapy until replacement device is provided. It is recommended to keep syringes, insulin pens and insulin cartridges on hand as back-up.

**Pump start, pump settings**

Guidelines on how to start a patient on the insulin pump will be provided to investigation sites, and this document will be kept separately from the CIP.

**Visit 3 – visit during pregnancy: 24th week (± 2 weeks window)**

- Ask patient to complete the HFS, DTSQs and DTSQc questionnaires
- Weigh the patient
- Measure the patient's blood pressure
- Collect the patient's medical data listed in the relevant eCRF
- Make therapy adjustment, and change pump settings, if necessary
- Check infusion site, make sure patient uses infusion sets properly
- Fill in the eCRF and submit the data
- Upload data into CareLink Clinical from the insulin pump (and BG meter, if applicable)

**Visit 4 – visit during pregnancy: 36th week (± 2 weeks window)**

- Ask patient to complete the HFS and DTSQs questionnaires
- Weigh the patient
- Measure the patient's blood pressure
- Collect the patient's medical data listed in the relevant eCRF
- Make therapy adjustment, and change pump settings, if necessary
- Check infusion site, make sure patient uses infusion sets properly
- Fill in the eCRF and submit the data
- Upload data into CareLink Clinical from the insulin pump (and BG meter, if applicable)

**Visit 5 – optional visit after delivery (+ 2 weeks window)**

- Weigh the patient before and after delivery
- Collect the delivery data listed in the relevant eCRF
- Collect the neonatal outcome data listed in the relevant eCRF
- Fill in the eCRF and submit the data
- Upload data into CareLink Clinical from the insulin pump (and BG meter, if applicable)

**Visit 6 – 6 weeks after delivery (± 2 weeks window)**

- Ask patient to complete the HFS and DTSQs questionnaires
- Weigh the patient
- Measure the patient's blood pressure

This document is electronically controlled. Printed copies are considered uncontrolled.

**Confidential**

- Collect the patient's medical data listed in the relevant eCRF
- Fill in the eCRF and submit the data
- Upload data into CareLink Clinical from the insulin pump (and BG meter, if applicable)
- Terminate pump therapy

**Miscarriage – any time**

- Weigh the patient
- Measure the patient's blood pressure
- Collect the patient's medical data listed in the relevant eCRF
- Discuss with patient if she wants to continue the same therapy (CSII or SAP)
- Check infusion site, make sure patient uses infusion sets properly (if applicable)
- Make therapy adjustment, and change pump settings, if necessary
- Fill in the eCRF and submit the data
- Upload data into CareLink Clinical from the insulin pump (and BG meter, if applicable)

**Early dropout – any time**

- Ask patient to complete the HFS and DTSQs questionnaires, if patient agrees
- Weigh the patient
- Measure the patient's blood pressure
- Collect the patient's medical data listed in the relevant eCRF
- Discuss with patient if she wants to continue the same therapy (CSII or SAP)
- Check infusion site, make sure patient uses infusion sets properly (if applicable)
- Make therapy adjustment, and change pump settings, if necessary
- Fill in the eCRF and submit the data
- Upload data into CareLink Clinical from the insulin pump (and BG meter, if applicable)

**Inclusion Criteria:**

A subject is eligible for the study if the following criteria are met:

1. Female diagnosed with Diabetes Mellitus Type 1
2. Subject indicated by HCP to start insulin pump therapy (CSII) or sensor augmented pump therapy (SAP) due to the desired or established pregnancy
3. HCP has prescribed the use of Orchestra donated device to the subject independently of the study
4. Signed Patient Informed Consent (PIC)
5. Subject is 18 to 45 years old, planning immediate pregnancy (within the next 12 months) or being pregnant within the first trimester until the 16th week of amenorrhea
6. Subject has been on MDI for at least 3 months before starting pump therapy

**Exclusion Criteria:**

A subject is excluded from the study if any of the following criteria are met:

1. Subject was enrolled in the registry earlier, and terminated it (for any reason)

This document is electronically controlled. Printed copies are considered uncontrolled.

**Confidential**

2. Participation in any other interventional clinical trial – currently and/or in the last 3 months before the signature of PIC
3. Subject uses an insulin pump that was not donated by the Orchestra Foundation
4. Pregnant women with longer than 16 weeks of pregnancy/amenorrhea
5. Subjects who need assisted in vitro fertilization
6. Subjects with Diabetes Mellitus Type 2, Gestational Diabetes, MODY or any other type of diabetes than Type 1
7. Subject under the age of 18
8. Subject legally incompetent
9. Subject cannot read or write

### Study Endpoints:

Data will be collected during routine follow-up visits from pre-conception time, during pregnancy and delivery, up to 6 weeks after delivery and at miscarriage, if any. Some endpoints as described below will be collected from patient medical files retrospectively up to 12 months prior to study start.

### Maternal outcomes

- HbA1c (local laboratory) – last value before insulin pump therapy started (retrospective value from patient's medical file), 2-3 values during pregnancy, and one value at the end of the study.
- Proportion of women achieving HbA1c <6.0%, 6.5%, 7%, 7.5% and 8% at each trimester
- Serious adverse events
  - Severe hypoglycaemia (according to the standard definition requiring third party assistance – see point F 5. 1) from the period of 12 months prior to study start until study end
  - DKA from the period of 12 months prior to study start until study end
  - Miscarriage, hospitalization because of uterine bleeding, hospitalization because of instable glycaemia and others
  - Any hospital admission
- Weight, BMI
- Daily insulin use
- Medical information: Microalbumin excretion with albumin/creatinin ratio, blood pressure, parity, folic acid and any other supplementation, White classification, diabetes duration, previous insulin regimen
- Number of SMBG/day (patient self-reported)
- Patient questionnaires:
  - Hypoglycaemia Fear Survey (HFS) collected at enrollment, 2-3 x during pregnancy, and 6 weeks after delivery
  - Diabetes Treatment Satisfaction Questionnaire (DTSQs, status version), collected at enrollment, 2-3 x during pregnancy, and 6 weeks after delivery, and Diabetes Treatment Satisfaction Questionnaire (DTSQc, change version), collected at 24 weeks into pregnancy
- Device Data:
  - Descriptive statistics for SMBG and SG (mean, SD, median, min and max)
  - time spent SG < 50 mg/dL
  - time spent SG between 50-70 mg/dL

This document is electronically controlled. Printed copies are considered uncontrolled.

**Confidential**

- time spent SG between 70-120 mg/dL
- time spent SG between 120-140 mg/dL
- time spent SG > 140 mg/dL
- time spent SG > 180 mg/dL
- AUC (SG < 70 mg/dl, SG > 180 mg/dl)
- MAGE
- All these parameters daily, 2-hour postprandial and during night (10PM to 7AM)
- Pump Compliance
- Sensor Compliance, if necessary.

### **Delivery information**

- Sensor and pump wear during delivery (yes/no)
- Patient satisfaction with treatment during delivery

### **Neonatal outcomes**

- Mode of delivery (rates elective and emergency Caesarean Section, normal)
- Respiratory distress (1 and 5 minute Apgar scores)
- Gestational age at delivery, % preterm delivery < 37 weeks
- Infant birth weight (SD scores and customised birth weight percentile, % large for gestational age (LGA), % small for gestational age (SGA))
- Neonatal morbidity (treatment for neonatal hypoglycaemia)
- Neonatal care admission (duration of stay, level of care)
- Pregnancy related Serious Adverse Events (miscarriage < 22 weeks, congenital malformation, stillbirth, neonatal death)
- Feeding at hospital discharge (breast, bottle, both)

Timing of data collection into eCRF:

[figure not shown]
- Baseline
- End of conception trial or after 12 months
- Pregnancy start
- 3 months of pregnancy (12 weeks of amenorrhea  $\pm$  4 weeks)
- 6 months of pregnancy (24 weeks of amenorrhea  $\pm$  2 weeks)
- 9 Months of pregnancy (36 weeks of amenorrhea  $\pm$  2 weeks)
- Delivery (+ 2 weeks)
- 6 weeks after delivery ( $\pm$  2 weeks)
- Miscarriage any time

### **Clinical Procedures:**

**Figure 1: Flow chart of the Enrollment and Termination possibilities depending on the pregnancy**

This document is electronically controlled. Printed copies are considered uncontrolled.

**Confidential**

## 6. Determination of Sample Size

The minimum number of subjects to be enrolled is 100 women with complete follow-up of pregnancy from pre-conception until 6 weeks after delivery. Based on local data and experience, complete follow-up from the pre-conception phase will be possible for about 1/3 of the pregnancies. In about 2/3 of the cases, CSII will start during the first trimester of pregnancy, at the latest on the 16th week.

The expected total sample size is therefore 500 subjects including

- 100 subjects with complete follow-up – all phases on CSII, including SAP (pre-conception, pregnancy, 6 weeks after delivery).
- 300 subjects with pregnancy (enrollment up to the 16th week of pregnancy) and 6 weeks after delivery
- 100 subject with early termination (for various reasons like miscarriage, no conception within 12 months, etc.)

Enrollment will stop when data from 100 pregnancies with complete follow-up from pre-conception until 6 weeks after delivery have been collected.

This document is electronically controlled. Printed copies are considered uncontrolled.

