- Approximately 2/3 of the study subjects will be provided with the Paradigm REAL-Time (stand-alone pump therapy, CSII), and rest of the subjects will be provided with the Paradigm Veo, MiniLink transmitter and sensors (sensor augmented pump therapy - SAP). The decision about the type of treatment is made by the Health Care Professional (HCP) together with the patient independently of the study. It is advised to choose sensor augmented pump therapy for patients who present overall good compliance and ability to understand and use such a therapy, as assessed by the treating physician.
- MiniLinks and sensors are provided free of charge mainly to Paradigm Veo users, from the pre-conception period until one month after delivery, ideally with wearing the sensor during delivery. For all planned deliveries with the sensor-augmented Paradigm pumps, the sensor should be ideally started 2 to 3 days before the delivery.
- Patients on the sensor-augmented Paradigm pumps can get as many sensors free of charge as recommended by their HCPs.
- Patients on the Paradigm REAL-Time without free of charge MiniLinks donated by the Orchestra Foundation can use Continuous Glucose Monitoring (MiniLink and sensors) to their own desire and costs, if agreed with the HCP.
- Patients attend regular routine follow-up without special requirements, where medical information is being collected in the eCRF system and the data from devices (pumps and meters) is being uploaded into CareLink Clinical.
- Women with miscarriage can keep their pump for additional 3 months after the miscarriage, if they want to continue the therapy.

Subject Population

The study will collect data until a minimum of 100 pregnancies with full follow-up on CSII or SAP are completed including the pre-conception period, pregnancy, and 6 weeks after delivery. The expected number of subjects to be enrolled is 500 in 30 diabetes centers in Poland, so that data from 100 pregnancies with complete follow-up could be collected. The study will stop when the 100 complete pregnancies have been completed, and followed up until 6 weeks after delivery.

Subject's participation will include up to 6 visits in up to 22 months for subject enrolled at the planning stage and followed until 6 weeks after delivery.

Inclusion Criteria

A subject is eligible for the study if the following criteria are met:

- Female diagnosed with Diabetes Mellitus Type 1

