The minimum number of subjects to be enrolled is 100 women with complete follow-up of pregnancy from pre-conception until 6 weeks after delivery. Based on local data and experience, complete follow-up from the pre-conception phase will be possible for about 1/3 of the pregnancies. In about 2/3 of the cases, CSII will start during the first trimester of pregnancy, at the latest on the 16th week.

The expected total sample size is therefore 500 subjects including

- 100 subjects with complete follow-up – all phases on CSII, including SAP (pre-conception, pregnancy, 6 weeks after delivery).
- 300 subjects with pregnancy (enrollment up to the 16th week of pregnancy) and 6 weeks after delivery
- 100 subject with early termination (for various reasons like miscarriage, no conception within 12 months, etc.)

Enrollment will stop when data from 100 pregnancies with complete follow-up from pre-conception until 6 weeks after delivery have been collected.

C.7 Number of investigation sites and study duration

The Orchestra Foundation identified up to 30 sites in Poland to which they decided to make the pump donation (See the attached list, Annex L2.2).

The expected minimum number of subjects per investigation site is 2, the maximum number is 70. The numbers of subjects from the particular sites are based on the geography, potential, and level of experience of the site.

The time period for enrollment is 30 months, and started in May 2013. The treatment period is up to 22 months depending on in which phase of pregnancy the subject is enrolled. Data is collected at the beginning, during and at the end of the treatment period. Final report of the study is expected in 2018.

Table 1: Timelines of the study

| Project /Task | Start | End |
|---|----------------------------------|----------------------------------|
| Clinical study | Nov 2012 | Dec 2017 |
| 
 • Kick-off • Enrollment • End of study | Nov 2012 May 2013 Feb 2017 | Nov 2012 Dec 2015 Dec 2017 |
| Data | May 2013 | Dec 2017 |
| 
 • Data collection • • • Preliminary results • Data processing | May 2013 2017 Dec 2017 | Dec 2017 2017 Feb 2018 |
| Publication | Early 2018 | End 2018 |

D SUBJECT SELECTION

D.1 Inclusion criteria

A subject is eligible for the study if the following criteria are met:

1. Female diagnosed with Diabetes Mellitus Type 1

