## **5. Investigation Plan**

### **Study design:**

The project is designed as a multi-center prospective observational Post-Market-Release study to be conducted in up to 30 centers in Poland.

Total duration of the study per patient will be up to 22 months (up to 12 months pre-conception phase, pregnancy, and 6 weeks after delivery). The optimal study start is the beginning of pre-conception phase, however, pregnant women up to the 16th week of pregnancy can participate in the study too. The study end is 6 weeks after delivery. If conception does not occur within 12-months, the patient's study participation is terminated, and the insulin pump might be taken away from the patient. The following therapy is decided by the investigator. If the pump is not taken away after the 12-month of trial period for conception, the patient can continue insulin pump therapy until the pump is needed for another patient.

The study started in May 2013; enrolment period is planned for 30 months which can be modified by the decision of the Steering Committee. The final report will be available within 24 months after the end of enrolment.. Data collection will be stopped when data have been collected from 100 pregnancies with complete follow-up (including pre-conception phase, pregnancy, delivery and 6 weeks of lactation).

This document is electronically controlled. Printed copies are considered uncontrolled.

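### At the 100th complete case the plan variously stops enrolment, data collection or the study, without saying what happens to women still in follow-up; and the total of 500 does not follow from the stated one-third

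*SAP*

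**What the plan says.** **Sample size.** SAP section 6 and protocol C.6 carry the same text. It sets a floor: "The minimum number of subjects to be enrolled is 100 women with complete follow-up of pregnancy". It then says that "complete follow-up from the pre-conception phase will be possible for about 1/3 of the pregnancies" and that in about two-thirds of cases pump therapy starts in the first trimester, by week 16 at the latest. From this it concludes that 500 subjects are expected, in three strata: 100 with complete follow-up, "300 subjects with pregnancy (enrollment up to the 16th week of pregnancy) and 6 weeks after delivery", and 100 early terminations (miscarriage, no conception within 12 months, and so on).

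**What happens at the 100th complete case.**
- SAP section 6 and protocol C.6: "Enrollment will stop when data from 100 pregnancies with complete follow-up from pre-conception until 6 weeks after delivery have been collected".
- SAP section 5 (Study design) and protocol Synopsis (Design): "Data collection will be stopped when data have been collected from 100 pregnancies with complete follow-up".
- Protocol Synopsis (Subject Population): "The study will stop when the 100 complete pregnancies have been completed, and followed up until 6 weeks after delivery". The same paragraph also says "The study will collect data until a minimum of 100 pregnancies with full follow-up on CSII or SAP are completed".

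**Calendar.** Protocol Table 1 (C.7) gives end dates for kick-off, enrolment and end of study of "Nov 2012 Dec 2015 Dec 2017", and data collection also runs to December 2017. The enrolment period is stated as 30 months from May 2013, which the Steering Committee may modify. Protocol G.4 places close-out after all patient follow-ups are complete. Protocol F.7 replaces withdrawn subjects until 100 full follow-ups are reached and gives no date.

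**The concern.** The word linking the one-third to the 500 claims a derivation, but the strata printed below it imply a different fraction. A reader cannot tell which premise the sponsor used.

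The stop rule matters more. Women may enrol until the trigger is reached. If data collection ends at that same moment, those who entered shortly before it are cut off by construction. A pre-conception entrant needs between about 10 months (immediate conception) and 22 months (conception after the full 12) to become a complete case, so slower conceivers would be lost selectively, together with late entrants of either kind. The data lost would be later-pregnancy glycaemia, delivery and neonatal outcomes, which serve both the primary and secondary objectives. SAP 7.1.3 keeps all enrolled women in the analysis, SAP 7.4 imputes nothing, and SAP 7.9 stratifies sensor and meter glucose by completeness of treatment phase. Women cut off administratively could therefore share a stratum with women who miscarried or stopped early.

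**Working it through.** **Part 1: the 500.**

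Inputs (SAP section 6, protocol C.6): 100 complete cases; share about 1/3; 100 early terminations; printed strata 100 + 300 + 100.

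1. The plan's own total: 100 + 300 + 100 = 500. The strata add up.
2. Total from the stated share: 100 ÷ (1/3) = 300 pregnancies, of which 200 are enrolled when pregnant. Adding 100 early terminations gives 400, not 500.
3. Share implied by the printed strata: 100/400 = 1/4 and 300/400 = 3/4 of pregnancies followed through.
4. The word about does not close the gap. Using 100/share + 100: a share of 0.30 gives 433, 0.35 gives 386, and 500 needs exactly 0.25.
5. Can 500 be reconciled with 1/3 and 2/3? Yes, if the fractions describe who enters.
   - *All enrolled women:* 500/3 = 167 pre-conception and 333 pregnant entrants. Early terminations are then 167 − 100 = 67 (40%) and 333 − 300 = 33 (10%).
   - *All pregnancies, including those that end early:* let x be early-ending pregnancies among pre-conception entrants, y early endings among pregnant entrants, and z women never pregnant, with x + y + z = 100. Then (100 + x)/(400 + x + y) = 1/3 gives y = 2x − 100, so x runs from 50 to 66.7, y from 0 to 33.3 and z from 50 to 0. At x = 50, pre-conception terminations are 50 + 50 = 100 of 200 (50%) and pregnant-entrant terminations are 0 of 300.
   
   The documents give no split of the 100. These values only show that it is open.
6. Under either reading, complete follow-up is at most 100/400 = 1/4 of pregnancies. It is 100/450 = 22% if 50 of the early terminations are pregnancies, and 100/500 = 20% if all are.

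**Part 2: the stop rule.** No formula applies, so the passages are set side by side.

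| Place | At the 100th complete case | Women still in follow-up |
|---|---|---|
| SAP 6, protocol C.6 | enrolment stops | silent |
| SAP 5, Synopsis (Design) | data collection stops | cut off if literal |
| Synopsis (Subject Population) | study stops | cut off if literal |
| Table 1, G.4 | calendar dates; close-out after all follow-ups | followed to the end |

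Stopping data collection at the 100th case would also turn the stated minimum of 100 into a maximum.

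Time each woman needs after entry:
- Pre-conception entrant: up to 22 months; 22 − 12 = 10 months if conception is immediate.
- Woman entering at week 16: 37 − 16 + 6 = 27 weeks to 40 − 16 + 6 = 30 weeks, assuming delivery at weeks 37 to 40.

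Does following everyone fit the calendar? 31 Dec 2015 + 22 months = 31 Oct 2017. Adding the 2-week Visit 6 window gives 14 Nov 2017, and adding 4 weeks for eCRF submission (protocol G.1.2) gives 12 Dec 2017. That is inside data collection to December 2017.

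One side discrepancy: 30 months starting in May 2013 end in October 2015, whereas Table 1 runs enrolment to December 2015, which is 32 months.

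**The case against.** **On the 500.** The one-third sentence can be read as describing entry before conception, and then 500 is reachable. That stands, and it is why the total cannot be called wrong. It does not rescue the text, because the split it needs is nowhere stated. No test or power depends on the number (SAP 7.2).

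**On the stop rule.** SAP section 6 does not say that only enrolment stops, nor that follow-up continues. One event could close both enrolment and data collection, so the sentences are unreconciled rather than flatly contradictory. This stands. The silence is itself the gap, because Table 1 and G.4 assume follow-up that no sentence secures.

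**On intent.** The Design paragraph that stops data collection also sets each woman's study end at 6 weeks after delivery and allows 24 months from the end of enrolment to the final report, which leaves room for 22 months of follow-up. Planned truncation is an unlikely intention. This also stands, and it makes the harm conditional.

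**On pooling with true terminations.** The reason for withdrawal is recorded in the eCRF and study discontinuation is a listed reason (protocol F.3 and F.7). SAP 7.1.1 reports withdrawals and completion of each phase, and the SAP version history adds a table of withdrawal reasons. Administrative cut-offs could therefore be identified. What remains is that the strata in SAP 7.9 are defined by phase completed, with no stated rule to separate them.

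**A figure a reader might infer.** Applying one-third to the printed 400 pregnancies gives 133 complete cases, suggesting 33 lost beyond the 100th. The documents do not support this, because it pairs two premises that exclude each other. The printed strata give 100 complete cases, and so does a literal one-third of 300, so neither yields any beyond the 100th.

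**Conclusion.** Both inconsistencies are in the current text of both documents.

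The sample-size part is minor: one-quarter and three-quarters printed against one-third and two-thirds stated, and 500 printed against 400 from the literal share. It would go too far to conclude that 500 is wrong. It is unsupported as derived, and it fits an entry-based reading once an unstated split of early terminations is supplied.

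The stop rule is the part that should be fixed. One trigger has three stated consequences, and no passage says which governs. If the data-collection or study-stop sentence is followed literally, outcome data for women still in follow-up are lost, selectively among late entrants and slow conceivers. The number depends on accrual, which the documents do not give. It is zero if Table 1 and G.4 are followed. No loss is demonstrated; the plan merely permits one.

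A reader might also infer that enrolment should close on the Table 1 date whatever the count. The documents do not support that either: the 100-case minimum, the enrolment trigger and the replacement rule are all driven by completions, and the enrolment period can be modified.

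**What to change.** 1. **Stop rule.** Replace the stop sentences in the protocol Synopsis (Design and Subject Population) and SAP section 5, and add to protocol C.6 and SAP section 6:

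   > Reaching 100 complete cases closes enrolment only; data for every woman already enrolled are collected to her own protocol-defined study end (6 weeks after delivery, or earlier termination).

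2. **Calendar.** The sponsor should reconcile the 100-case trigger and the replacement rule in F.7 with the Table 1 dates and the 30-month period, and print one planned closing date. Whether enrolment may close on a date before 100 complete cases is a decision for the sponsor and Steering Committee and is not part of this change.

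3. **Sample size.** Keep 500 as the expected total. Either restate the shares as about one-quarter and three-quarters of pregnancies followed through, or state the denominator of the one-third and, from the local data, the split of the 100 early terminations.

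**Cost.** Changes to text in both documents; no added subjects. Data collection may run up to about 22 months after the last enrolment. That fits the December 2017 end if enrolment closes by December 2015; if enrolment is extended, the end of data collection has to move with it.
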